6.1 Atezolizumab (MPDL3280A)

6.1.1 General AE Management and Dose Modification Guidelines

There will be no dose reduction for atezolizumab in this study.

Patients may temporarily suspend study treatment for up to 84 days (12 weeks) beyond the scheduled date of delayed infusion if study drug-related toxicity requiring dose suspension is experienced. If atezolizumab is held because of AEs for >84 days beyond the scheduled date of infusion, the patient will be discontinued from atezolizumab and will be followed for safety and efficacy as specified in this protocol. If the AE resolves within 84 days and the patient is receiving corticosteroid therapy for the event, atezolizumab may be held for longer than 84 days (up to 4 weeks) in order to allow tapering of the steroid dose to ≤ 10 mg oral prednisone or equivalent.

Dose interruptions for reasons other than toxicity, such as surgical procedures, may be allowed. The acceptable length of interruption will be at the discretion of the study PI in consultation with CTEP.

For detailed information regarding management of AEs associated with atezolizumab, please refer to the most current version of the Atezolizumab Investigator's Brochure and the FDA product label.

The primary approach to grade 1 to 2 irAEs is supportive and symptomatic care with continued treatment with atezolizumab; for higher-grade irAEs, atezolizumab should be withheld and oral and/or parenteral steroids administered. Recurrent grade 2 irAEs may also mandate withholding atezolizumab or the use of steroids. Assessment of the benefit-risk balance should be made by the investigator, with consideration of the totality of information as it pertains to the nature of the toxicity and the degree of clinical benefit a given patient may be experiencing before further administration of atezolizumab.

Atezolizumab should be permanently discontinued in patients with life-threatening irAEs.

Patients should be assessed clinically (including review of laboratory values) for toxicity before, during, and after each infusion. If unmanageable toxicity due to atezolizumab occurs at any time during the study, treatment with atezolizumab should be discontinued.

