6.1.2.4 Endocrine disorders

Thyroid disorders, adrenal insufficiency, diabetes mellitus, and pituitary disorders have been associated with the administration of atezolizumab. Management guidelines for endocrine events are provided in the table below

Patients with unexplained symptoms such as headache, fatigue, myalgias, impotence, constipation, or mental status changes should be investigated for the presence of thyroid, pituitary, or adrenal endocrinopathies. The patient should be referred to an endocrinologist if an endocrinopathy is suspected. Thyroid stimulating hormone (TSH) and free triiodothyronine (T3) and thyroxine (T4) levels should be obtained to determine whether thyroid abnormalities are present. Pituitary hormone levels and function tests (*e.g.*, TSH, growth hormone, luteinizing hormone, follicle-stimulating hormone, testosterone, prolactin, adrenocorticotropic hormone

[ACTH] levels, and ACTH stimulation test) and magnetic resonance imaging (MRI) of the brain (with detailed pituitary sections) may help to differentiate primary pituitary insufficiency from primary adrenal insufficiency.

Event	Management
Asymptomatic hypothyroidism	
Continue atezolizumab.Initiate treatment with thyroid replacement hormone.Monitor TSH closely.
Symptomatic hypothyroidism	
Withhold atezolizumab.Initiate treatment with thyroid replacement hormone.Monitor TSH closely.Consider patient referral to endocrinologist.Resume atezolizumab when symptoms are controlled and thyroid function is improving.
Asymptomatic hyperthyroidism	
TSH \geq0.1 mU/L and <0.5 mU/L:
 
Continue atezolizumab.Monitor TSH every 4 weeks.Consider patient referral to endocrinologist. 
TSH <0.1 mU/L:
 
Follow guidelines for symptomatic hyperthyroidism.Consider patient referral to endocrinologist.
Symptomatic hyperthyroidism	
Withhold atezolizumab.Initiate treatment with anti-thyroid drug such as methimazole or carbimazole as needed.Consider patient referral to endocrinologist.Resume atezolizumab when symptoms are controlled and thyroid function is improving.Permanently discontinue atezolizumab.^c

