Symptomatic adrenal insufficiency, Grade 2–4	
Withhold atezolizumab for up to 12 weeks after event onset.^aRefer patient to endocrinologist.Perform appropriate imaging.Initiate treatment with corticosteroids equivalent to 1–2 mg/kg/day IV methylprednisolone and convert to 1–2 mg/kg/day oral prednisone or equivalent upon improvement.If event resolves to Grade 1 or better and patient is stable on replacement therapy, resume atezolizumab.^bIf event does not resolve to Grade 1 or better or patient is not stable on replacement therapy while withholding atezolizumab, permanently discontinue atezolizumab.^c

Hyperglycemia, Grade 1 or 2	
Continue atezolizumab.Investigate for diabetes. In the absence of corticosteroids or diabetes medication non-adherence may be an indication of beta-cell destruction and atezolizumab-induced diabetes. If patient has Type 1 diabetes (e.g. new-onset diabetes in the absence of corticosteroids or another inciting medication), treat as a Grade 3 event.Exercise caution in utilizing non-insulin hypoglycemic agents in this setting, as new-onset hyperglycemia in the absence of corticosteroids may be an indication of beta-cell destruction and atezolizumab-induced diabetes. After a thorough investigation of other potential causes which may involve a referral to an endocrinologist, follow institutional guidelines.Monitor for glucose control.
Hyperglycemia, Grade 3 or 4	
Withhold atezolizumab.Initiate treatment with insulin.Monitor for glucose control.Strongly consider referral to endocrinologist, particularly if patient is deemed to have atezolizumab-induced diabetes; if so, obtain C-peptide level paired with glucose, autoantibody levels (e.g. GAD65, islet cell autoantibodies), and hemoglobin A1C level.If patient is found to have diabetic ketoacidosis or hyperglycemic hyperosmolar syndrome, treat as per institutional guidelines with appropriate management and laboratory values (e.g. anion gap, ketones, blood pH, etc.) reported.Resume atezolizumab when symptoms resolve and glucose levels are stable.

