Hypophysitis (pan-hypopituitarism), Grade 2 or 3	
Withhold atezolizumab for up to 12 weeks after event onset.^aRefer patient to endocrinologist.Perform brain MRI (pituitary protocol).Initiate treatment with corticosteroids equivalent to 1-2 mg/kg/day IV methylprednisolone and convert to 1-2 mg/kg/day oral prednisone or equivalent upon improvement.Initiate hormone replacement if clinically indicated.If event resolves to Grade 1 or better, resume atezolizumab.^bIf event does not resolve to Grade 1 or better while withholding atezolizumab, permanently discontinue atezolizumab.^cFor recurrent hypophysitis, treat as a Grade 4 event.
Hypophysitis (pan-hypopituitarism), Grade 4	
Permanently discontinue atezolizumab.^cRefer patient to endocrinologist.Perform brain MRI (pituitary protocol).Initiate treatment with corticosteroids equivalent to 1-2 mg/kg/day IV methylprednisolone and convert to 12 mg/kg/day oral prednisone or equivalent upon improvement.Initiate hormone replacement if clinically indicated.

MRI = magnetic resonance imaging; TSH = thyroid-stimulating hormone.

^a Atezolizumab may be withheld for a longer period of time (*i.e.*, >12 weeks after event onset) to allow for corticosteroids (if initiated) to be reduced to the equivalent of ≤ 10 mg/day oral prednisone. The acceptable length of the extended period of time must be based on an assessment of benefit–risk by the investigator and in alignment with the protocol requirements for the duration of treatment and documented by the investigator.

^b If corticosteroids have been initiated, they must be tapered over ≥ 1 month to the equivalent of ≤ 10 mg/day oral prednisone before atezolizumab can be resumed.

^c Resumption of atezolizumab may be considered in patients who are deriving benefit and have fully recovered from the immune-mediated event. The decision to re–challenge patients with atezolizumab should be based on investigator's assessment of benefit–risk and documented by the investigator (or an appropriate delegate).

6.1.2.5 *Ocular Events*

An ophthalmologist should evaluate visual complaints (*e.g.*, uveitis, retinal events).

Management guidelines for ocular events are provided in the table below.

Event	Management

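### The symptomatic hyperthyroidism entry in section 6.1.2.4 tells sites both to resume atezolizumab and, with no condition, to stop it permanently

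*Combined protocol and SAP*

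**What the plan says.** The symptomatic hyperthyroidism entry in section 6.1.2.4 gives five instructions in order:

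1. Withhold atezolizumab.
2. "Initiate treatment with anti-thyroid drug such as methimazole or carbimazole as needed".
3. Consider referral to an endocrinologist.
4. "Resume atezolizumab when symptoms are controlled and thyroid function is improving".
5. "Permanently discontinue atezolizumab.^c"

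The fifth carries footnote mark c and nothing else. Footnote c reads in part: "Resumption of atezolizumab may be considered in patients who are deriving benefit and have fully recovered from the immune-mediated event". It leaves that decision to the investigator's documented benefit–risk assessment.

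In the asymptomatic hyperthyroidism entry, the sub-row for TSH below 0.1 mU/L says "Follow guidelines for symptomatic hyperthyroidism". The sub-row for TSH from 0.1 to below 0.5 mU/L continues treatment and does not point there.

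The general rules in section 6.1.1 continue treatment with supportive care for grade 1 to 2 immune-related events, withhold for higher grades, and stop for unmanageable toxicity. They also say: "Atezolizumab should be permanently discontinued in patients with life-threatening irAEs".

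**The concern.** Instructions 4 and 5 give opposite directions for the same patient. A patient whose symptoms settle on an anti-thyroid drug meets the condition for resuming, yet the next line says to stop for good. Through the cross-reference, a patient with suppressed TSH and no symptoms inherits the same pair.

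What is at stake is how patients are managed. Read literally, the last line would permanently end atezolizumab in someone with controlled or symptom-free hyperthyroidism, which goes further than section 6.1.1. Sites could also handle the same event differently. Atezolizumab is given in both arms (section 5.1.1), and section 7.3.5 lists hyperthyroidism as an event of special interest needing expedited reporting, so sites can be expected to consult this entry.

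**Working it through.** The plan gives no figure to reproduce here. The check compares the entry with its neighbours, its footnote, the general rules and the other management tables.

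**Same table (section 6.1.2.4)**

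| Entry | Restart instruction | Permanent discontinuation |
|---|---|---|
| Symptomatic hypothyroidism | When symptoms are controlled and function is improving | None |
| Symptomatic hyperthyroidism | Same as hypothyroidism | Stated, with no condition |
| Symptomatic adrenal insufficiency, Grade 2–4 | On resolution to Grade 1 or better and stable on replacement | If not resolved, or if "patient is not stable on replacement therapy while withholding atezolizumab, permanently discontinue atezolizumab" |
| Hypophysitis, Grade 2 or 3 | On resolution to Grade 1 or better | If not resolved |
| Hypophysitis, Grade 4 | None | Trigger is the grade in the row label |

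Only the hyperthyroidism entry has both a restart line and an untriggered stop.

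**Footnote c.** The resume instruction needs controlled symptoms and improving thyroid function. The footnote needs full recovery and benefit, and even then resumption is only something that may be considered. A patient controlled on methimazole can pass the first test and fail the second. The footnote also does not say when to discontinue.

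**Section 6.1.1.** This section reserves permanent discontinuation for life-threatening events and also stops treatment for unmanageable toxicity. Hyperthyroidism that is controlled or symptom-free is not, as such, either of these. The general rule therefore suggests which condition is missing, but a reader has to infer it.

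**All section 6.1.2 tables.** Entries that contain both a restart and a permanent-discontinuation instruction:

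- Pulmonary: 1 (Grade 2)
- Hepatic: 2 (Grade 2 without hepatocellular carcinoma; the transaminase entry with hepatocellular carcinoma, counted once although its lines are split in the extracted text)
- Gastrointestinal: 2 (Grades 2 and 3)
- Endocrine: 3 (symptomatic hyperthyroidism, adrenal insufficiency, hypophysitis Grade 2 or 3)
- Ocular: 1 (Grade 2)
- Infusion reaction or cytokine release: 1 (Grade 2, where the restart is worded as permission to give the next dose)
- Pancreatic: 2 (amylase or lipase Grade 3 or 4; pancreatitis Grade 2 or 3)
- Dermatologic: 1 (Grade 3)
- Neuropathy: 1 (Grade 2)
- Renal: 1 (Grade 2)
- Myositis: 2 (Grades 2 and 3)

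Total: 1 + 2 + 2 + 3 + 1 + 1 + 2 + 1 + 1 + 1 + 2 = 17. Sixteen state when discontinuation applies, usually failure to resolve to Grade 1 or better. The remaining one (17 − 16 = 1) is symptomatic hyperthyroidism.

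**Patients affected.** The risk list in section 7.1.1 places hyperthyroidism only in the band of at most 20%, with no split by symptoms or TSH, so no patient count can be derived.

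**The case against.** The strongest reply is that the harmful reading is strained. If every symptomatic case were to stop permanently, the instructions to withhold, treat and resume would serve no purpose, so a clinician reading the whole entry would probably suspect a lost qualifier. Section 6.1.1, in the same part of the protocol, supplies a graded rule that includes withholding for higher-grade events. Footnote c keeps the discontinuation from being absolute. This makes error at a site less likely. It does not make the entry usable as written: the reader must still supply a condition that the other 16 paired entries state.

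A second reply is that the detailed guidance lies in the Investigator's Brochure, to which sections 6.1.1 and 6.1.2 refer and which was not available for this check. The missing words could be a life-threatening limit or a non-resolution condition, or the line could be a stray. This is correct, and any replacement wording needs sponsor confirmation.

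A third is that a qualifier may have been lost when the PDF was read. The text of this part of the protocol has other blemishes; the hypophysitis Grade 4 row, for instance, gives 12 mg/kg/day where parallel rows give 1–2. Loss is possible but not indicated: the line is a complete sentence with a full stop and a footnote mark, and no gap or redaction is visible.

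Finally, the TSH sub-row is a pointer to the defect rather than a second defect. That is fair, and conditioning the last instruction would by itself make the pointer work.

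**Conclusion.** The concern holds. The symptomatic hyperthyroidism entry is wrong as written: it is an operative dosing rule with two incompatible instructions, and neither its footnote nor section 6.1.1 resolves them. One entry is directly defective, and the TSH below 0.1 mU/L sub-row inherits the problem.

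This should be corrected as a matter of patient management. It does not bear on response rate, progression-free or overall survival, sample size or error rates. Confidence is medium. The conclusion assumes that the extracted text of the entry is complete, and the life-threatening limit is an inference from section 6.1.1.

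**What to change.** Give the last instruction of the symptomatic hyperthyroidism entry a condition, for example: permanently discontinue atezolizumab for life-threatening immune-mediated hyperthyroidism. This agrees with section 6.1.1. The sponsor should confirm the clinical wording against the current Investigator's Brochure before it is adopted.

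For clarity, add to the TSH below 0.1 mU/L sub-row that the patient follows the withhold-and-resume path of the symptomatic entry. This second edit is helpful but not essential once the first is made.

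The cost is one instruction and one cross-reference in a single table. Design, sample size and analysis do not change.

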6.1.2.3 *Gastrointestinal events*

Immune-mediated colitis has been associated with the administration of atezolizumab. Management guidelines for diarrhea or colitis are provided in the table below.

All events of diarrhea or colitis should be thoroughly evaluated for other more common etiologies. For events of significant duration or magnitude or associated with signs of systemic inflammation or acute-phase reactants (*e.g.*, increased C-reactive protein, platelet count, or bandemia): Perform sigmoidoscopy (or colonoscopy, if appropriate) with colonic biopsy, with three to five specimens for standard paraffin block to check for inflammation and lymphocytic infiltrates to confirm colitis diagnosis.

Event	Management
Diarrhea or colitis, Grade 1	
Continue atezolizumab.Initiate symptomatic treatment.Endoscopy is recommended if symptoms persist for >7 days.Monitor closely.
Diarrhea or colitis, Grade 2	
Withhold atezolizumab for up to 12 weeks after event onset.^aInitiate symptomatic treatment.Patient referral to GI specialist is recommended.For recurrent events or events that persist >5 days, initiate treatment with corticosteroids equivalent to 1–2 mg/kg/day oral prednisone.If event resolves to Grade 1 or better, resume atezolizumab.^bIf event does not resolve to Grade 1 or better while withholding atezolizumab, permanently discontinue atezolizumab.^c

Event	Management
Diarrhea or colitis, Grade 3	
Withhold atezolizumab for up to 12 weeks after event onset.^aRefer patient to GI specialist for evaluation and confirmatory biopsy.Initiate treatment with corticosteroids equivalent to 1–2 mg/kg/day IV methylprednisolone and convert to 1–2 mg/kg/day oral prednisone or equivalent upon improvement.If event resolves to Grade 1 or better, resume atezolizumab.^bIf event does not resolve to Grade 1 or better while withholding atezolizumab, permanently discontinue atezolizumab.^c

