Amylase and/or lipase elevation, Grade 3 or 4	
Withhold atezolizumab for up to 12 weeks after event onset.^aRefer patient to GI specialist.Monitor amylase and lipase every other day.If no improvement, consider treatment with corticosteroids equivalent to 1–2 mg/kg/day oral prednisone.If event resolves to Grade 1 or better, resume atezolizumab.^bIf event does not resolve to Grade 1 or better while withholding atezolizumab, permanently discontinue atezolizumab.^cFor recurrent events, permanently discontinue atezolizumab.^c
Immune-mediated pancreatitis, Grade 2 or 3	
Withhold atezolizumab for up to 12 weeks after event onset.^aRefer patient to GI specialist.Initiate treatment with corticosteroids equivalent to 1–2 mg/kg/day IV methylprednisolone and convert to 1–2 mg/kg/day oral prednisone or equivalent upon improvement.If event resolves to Grade 1 or better, resume atezolizumab.^bIf event does not resolve to Grade 1 or better while withholding atezolizumab, permanently discontinue atezolizumab.^cFor recurrent events, permanently discontinue atezolizumab.^c

Event	Management
Immune-mediated pancreatitis, Grade 4	
• Permanently discontinue atezolizumab.^c• Refer patient to GI specialist.• Initiate treatment with corticosteroids equivalent to 1–2 mg/kg/day IV methylprednisolone and convert to 1–2 mg/kg/day oral prednisone or equivalent upon improvement.• If event does not improve within 48 hours after initiating corticosteroids, consider adding an immunosuppressive agent.• If event resolves to Grade 1 or better, taper corticosteroids over ≥ 1 month.

GI = gastrointestinal.

^a Atezolizumab may be withheld for a longer period of time (*i.e.*, >12 weeks after event onset) to allow for corticosteroids (if initiated) to be reduced to the equivalent of ≤ 10 mg/day oral prednisone. The acceptable length of the extended period of time must be based on an assessment of benefit–risk by the investigator and in alignment with the protocol requirements for the duration of treatment and documented by the investigator.

^b If corticosteroids have been initiated, they must be tapered over ≥ 1 month to the equivalent of ≤ 10 mg/day oral prednisone before atezolizumab can be resumed.

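### Section 6.1.2.4, Grade 4 hypophysitis: the oral prednisone step-down reads 12 mg/kg/day, where all 11 comparable rows of section 6.1.2 give 1-2 mg/kg/day

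*Combined protocol and SAP*

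**What the plan says.** The immune-related event tables in section 6.1.2 use a common steroid instruction for severe events: start IV methylprednisolone, then change to oral prednisone when the patient improves. In section 6.1.2.4 the row for hypophysitis Grade 2 or 3 gives "1-2 mg/kg/day IV methylprednisolone and convert to 1-2 mg/kg/day oral prednisone or equivalent upon improvement". The adrenal insufficiency row of the same table (Grade 2-4) also has the site "convert to 1–2 mg/kg/day oral prednisone or equivalent upon improvement".

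The hypophysitis Grade 4 row follows directly after the Grade 2 or 3 row. Its IV dose is also 1-2 mg/kg/day, but its oral prednisone dose is printed as 12 mg/kg/day. The Grade 2 or 3 row adds that recurrent hypophysitis is to be handled as Grade 4, so the Grade 4 dose applies to recurrences as well.

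**The concern.** The instruction contradicts itself within one sentence. A change to oral treatment made because the patient has improved should not carry a figure 6 to 12 times the IV starting figure. The likely cause is a missing hyphen or dash, turning 1-2 into 12.

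The cell is operative text: it sets a corticosteroid dose for a life-threatening immune-related event and for any recurrence. Taken literally, a site would give several times the dose that the protocol uses everywhere else. Unlike the Grade 4 colitis and pancreatitis rows, this row also has no line on tapering once the event resolves. The point concerns patient safety and the internal consistency of the protocol, not the statistical design.

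**Working it through.** No design figure has to be reproduced. The check is a complete comparison of the rows in section 6.1.2 that start IV methylprednisolone and then state an oral prednisone dose.

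| Section | Event and grade | Oral prednisone (mg/kg/day) | Covers Grade 4 |
|---|---|---|---|
| 6.1.2.3 | Diarrhea or colitis, 3 | 1-2 | no |
| 6.1.2.3 | Diarrhea or colitis, 4 | 1-2 | yes |
| 6.1.2.4 | Symptomatic adrenal insufficiency, 2-4 | 1-2 | yes |
| 6.1.2.4 | Hypophysitis, 2 or 3 | 1-2 | no |
| **6.1.2.4** | **Hypophysitis, 4** | **12** | **yes** |
| 6.1.2.6 | Myocarditis, 2-4 | 1-2 | yes |
| 6.1.2.8 | Pancreatitis, 2 or 3 | 1-2 | no |
| 6.1.2.8 | Pancreatitis, 4 | 1-2 | yes |
| 6.1.2.10 | Meningoencephalitis, all grades | 1-2 | yes |
| 6.1.2.13 | Myositis, 2 | 1-2 | no |
| 6.1.2.13 | Myositis, 3 | 1-2 | no |
| 6.1.2.13 | Myositis, 4 | 1-2 | yes |

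Rows that give an IV steroid without a stated oral conversion dose are left out: pulmonary Grade 3 or 4, infusion reactions and cytokine release, myasthenia gravis and Guillain-Barré syndrome, and HLH/MAS.

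**Count.** There are 12 rows. Apart from hypophysitis Grade 4 there are 11, and all 11 give 1-2. Six of those 11 cover Grade 4, and all six give 1-2.

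**Does severity explain it?** No. Besides the six Grade 4 rows, the Grade 3 and Grade 4 myositis rows are informative. They expressly allow a larger IV bolus for a severely compromised patient and still convert to 1-2 mg/kg/day by mouth. Where the protocol intends a higher dose it says so, and it leaves the oral step alone. No other oral prednisone dose in section 6.1.2 exceeds 2 mg/kg/day.

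**Size.** The ratio to the other rows is 12/2 = 6 up to 12/1 = 12. The daily dose depends on body weight, which is assumed here:

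| Assumed weight | As printed (12 × kg) | At 1-2 mg/kg/day |
|---|---|---|
| 60 kg | 720 mg | 60-120 mg |
| 80 kg | 960 mg | 80-160 mg |
| 100 kg | 1200 mg | 100-200 mg |

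**Exposure.** Section 7.1.1 lists hypophysitis for atezolizumab as rare but serious, below 3%. With 54 patients, 0.03 × 54 = 1.62, so fewer than about 1.6 cases of any grade would be expected if the combination has the same rate. The Grade 4 row applies only to Grade 4 and recurrent events, a subset for which the documents give no rate.

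**The case against.** The strongest objection is that the error may not exist on the issued page. The text was read from PDF by a program, and a hyphen falling at a line end could be dropped, joining 1 and 2 into 12. The type of dash matters. Both hypophysitis rows and the Grade 4 colitis row use a plain hyphen, whereas the other nine comparison rows use an en dash, which line-end joining would not normally remove. Only two of the 11 comparison rows therefore show a plain hyphen surviving. The 11 rows establish what dose was intended, not what the page prints. The same table also has an unconditional instruction to discontinue atezolizumab straight after one to resume it (symptomatic hyperthyroidism), which suggests that text was lost there, whether in authoring or in reading.

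This cannot be ruled out, but it is the less likely reading. The Grade 2 or 3 row has the same sentence in the same column, so it should wrap in the same place, and it kept both hyphens. The IV dose in the Grade 4 sentence kept its hyphen too. What stands is that the printed page must be checked first.

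The second objection is that the practical risk is small. A physician would probably notice the anomaly, the row requires referral to an endocrinologist, and sections 6.1.1 and 6.1.2 send sites to the Investigator's Brochure. That is fair and limits the priority, but none of it corrects the cell. The low expected count is not a firm ceiling either: section 7.1.2 warns that CYT107 in combination could exacerbate events known to be caused by the other agent.

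**Conclusion.** The concern holds on the text as supplied. The Grade 4 hypophysitis row gives an oral prednisone dose 6 to 12 times that in every comparable row, and nothing in the protocol supports it. The daily amounts rest on assumed weights of 60-100 kg; the exposure estimate rests on the atezolizumab rate carrying over to the combination. Confidence is medium, because the finding depends on a single character that could have been lost in reading the PDF. It should be corrected if the issued page confirms it, but it ranks below any design issue: no endpoint, analysis population or test is touched.

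**What to change.** Look at the hypophysitis Grade 4 cell in the issued protocol. If it prints 12, amend the oral step to match the row above, "convert to 1-2 mg/kg/day oral prednisone or equivalent upon improvement", and send sites a short notice so that no one works from the old figure. All 12 IV-to-oral rows would then agree. If the issued page already prints 1-2, nothing needs to change. The cost is one character in one table cell plus the notice; the statistical design is unaffected.
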